6.2. Data Conventions

The precision of original measurements will be maintained in summaries when possible.

For tables where rounding is required, rounding will be done at the final stage of the calculation, to the nearest round-off unit. For example, when rounding to the nearest integer, values $\geq XX.5$ will be rounded up to $XX + 1$ (eg, 97.5 will round up to 98), while values $< XX.5$ will be rounded down to XX (eg, 97.4 will round down to 97).

Percentages based on frequency counts will be based on available data, and denominators will generally exclude missing values, unless otherwise stated. For frequency counts of categorical variables, categories whose counts are 0 will be displayed for completeness. For example, if none of the patients discontinued due to “lost to follow-up,” this reason will be included in the table with a count of 0. Percentages based on frequency counts of eCRF collections

(eg, demographic categories) will be presented as a whole number (no decimal places), and nonzero values less than 0.5% will be presented as “<1%.” Values less than 100% but that round up from 99.5% to 100% will be presented as “>99%.”

Quantitative laboratory tests containing less than (<) and greater than (>) symbols are test results that are below and above quantifiable limits, respectively. In order to retain these values for analysis purpose, values will be imputed as the numeric portion of the result.

6.3. Analysis Populations

6.3.1. Full Analysis Set

All patients who are randomized and take at least 1 dose of double-blind study medication will be included in the Full Analysis Set (FAS). Patients in the FAS will be analyzed according to randomized treatment assignment. If a patient is incorrectly stratified (ie, randomized according to an incorrect stratification), the patient will be analyzed under the randomized treatment for the stratum recorded in the IWRS. All efficacy analyses for the double-blind period will be based on the FAS.

6.3.2. Interim Analysis Set

The IAS is the subset of the FAS at the time of the data extraction for interim analysis (per [Section 5.1](#)). Patients in the IAS will be analyzed according to randomized treatment assignment. All analyses conducted at the time of the interim analysis, including primary analysis of the surrogate endpoint and safety analysis, will be based on the IAS.

6.3.3. Per Protocol Analysis Set

The Per Protocol (PP) Analysis Set is a subset of the FAS containing patients who met study eligibility requirements and had no major protocol deviations that might affect the validity of the efficacy measurements. Patients will be analyzed according to randomized treatment assignment. The PP Analysis Set will be used for sensitivity analyses related to efficacy.

The criteria for inclusion in the PP Analysis Set will be finalized prior to study unblinding (interim and final) as specified in [Section 7.3](#). Evaluation of patient inclusion in the PP Analysis Set will occur for the interim analysis and final analysis.

6.3.4. Safety Analysis Set

The Safety Analysis Set includes all patients who are randomized and have taken at least 1 dose of study medication. Patients will be analyzed according to the double-blind randomized treatment. The Safety Analysis Set will be the primary population used for safety analyses.

6.3.5. Pharmacokinetic Analysis Set

The PK Analysis Set includes all patients who have received at least 1 dose of study medication and have at least 1 confirmed fasted analyzable sample. Patients must have been fasting for approximately 8 hours before the visit and must not have any major protocol deviations that potentially affect exposure levels. The PK Analysis Set will be used for PK and PK/pharmacodynamic analyses.

6.3.6. OLE Full Analysis Set

The OLE Full Analysis Set (OLEFAS) includes all patients who have received at least 1 dose of sparsentan in the open-label extension. All analyses during the OLE will be based on the OLEFAS. For the purposes of the analyses outlined in this SAP, patients will be analyzed according to randomized treatment assignment in the double-blind period.

6.4. Baseline Definition

6.4.1. Double-Blind Baseline

Double-blind baseline is defined as the last non-missing assessment prior to and including the first administration of study medication (including unscheduled assessments) in the study. In the case where the last non-missing assessment and the study medication start date (and time if available) coincide, that assessment will be considered baseline. Unless explicitly stated, all baselines used in this SAP will refer to the double-blind baseline.

6.4.2. Open-Label Extension Baseline

Open-label extension baseline is defined as the last non-missing assessment prior to and including the first administration of sparsentan (including unscheduled assessments) in the open-label extension. In the case where the last non-missing assessment and the sparsentan start date (and time if available) coincide, that assessment will be considered baseline.

6.5. Derived and Transformed Data

6.5.1. Baseline Age

Age is captured in the electronic data capture system, as relative to the date of informed consent.

6.5.2. Study Day

Study day 1 is defined as the day on which the first dose of study medication is administered (Day 1/Week 0). All other study days will be calculated relative to that date. The day before the start of study medication is Day -1 (there is no Day 0).

Study day will be calculated using the following formula:

study day = date – first dose date + 1, where date \geq first dose date

study day = date – first dose date, where date < first dose date

6.5.3. Standard Calculations

Variables requiring calculation will be derived using the following formulas:

- Days – A duration expressed in days between one date (*date1*) and another date (*date2*) will be calculated using the following formula:

$$\text{duration in days} = \text{date2} - \text{date1} + 1$$

- Months – A duration expressed in months is calculated as the number of days divided by 365.25/12 (approximately 30.4)
- Years – A duration expressed in years is calculated as the number of days divided by 365.25
- Height – Height entries made in inches (in) are converted to centimeters (cm) using the following formula:

$$\text{height (cm)} = \text{height (in)} \times 2.54$$

- Weight – Weight entries made in pounds (lb) are converted to kilograms (kg) using the following formula:

$$\text{weight (kg)} = \text{weight (lb)} / 2.2046$$

- Temperature – Temperature entries in degrees Fahrenheit are converted to degrees Celsius using the following formula:

$$\text{temp (degrees Celsius)} = 5 / 9 \times (\text{temp [degrees Fahrenheit]} - 32)$$

- Change from Baseline – Change from Baseline will be calculated as:

$$\text{Change} = \text{post Baseline value} - \text{Baseline value}$$

- Percentage change from Baseline – Change from Baseline will be calculated as:

$$\text{Percentage change from Baseline} = \left(\frac{\text{[post Baseline value} - \text{Baseline value]}}{\text{Baseline value}} \right) \times 100$$

- Percent Change from Baseline of variables analyzed in natural log will be calculated as:

$$\text{Percent Change} = [\exp(\text{change in natural log}) - 1] \times 100$$

For variables requiring log transformation, natural log will be used.

6.5.4. Visit Windows

A visit window method will be applied to determine analysis visits across the study for efficacy and safety endpoints based on laboratory results, including eGFR and quantitative urinalysis (including UP/C and FPFE). If a patient has multiple assessments (including unscheduled visits) within a visit window, the value closest to the target day for that visit will be selected for analysis. If more than 1 assessment is equidistant to the target day, then the latest value will be selected. For efficacy analysis visits on or prior to Week 108, only assessments while the patient is on randomized treatment should be included (see [Section 8.1](#) for definition of on treatment).

For quantitative urinalysis endpoints that are derived as the geometric mean of replicates collected over several days, all replicates used to derive the average should be mapped to the same analysis visit per Table 2, should be within 5 days of each other, and should all have been collected while the subject was on study medication. For the derivation of baseline, all replicates must have been collected on or prior to the date of reference dose. The study day of the endpoint will be derived as the maximum study day of the replicates used in the derivation.

If a patient is missing a UP/C assessment at a given analysis visit due to only having 1 urine sample available within 5 days, the available single assessment closest to the target day for that visit will be selected for sensitivity analysis.

The following visit windows for the double-blind period are defined for endpoints based on laboratory results. Visit windows for the OLE will be defined in a separate SAP.

Table 2: Visit Windows (Study Days)

Analysis Visit	Relative Target Day	Analysis Visit Window (Study Days)	
		eGFR and Safety Labs	Quantitative Urinalysis
Week 2	15	2 – 22	N/A
Week 4	29	23 – 36	N/A
Week 6	43	37 – 50	2 – 71
Week 8	57	51 – 71	N/A
Week 12	85	72 – 127	72 – 127
Week 24	169	128 – 211	128 – 211
Week 36	253	212 – 295	212 – 295
Week 48	337	296 – 379	296 – 379
Week 60	421	380 – 463	380 – 463
Week 72	505	464 – 547	464 – 547
Week 84	589	548 – 631	548 – 631
Week 96	673	632 – 715	632 – 715
Week 108 ¹	757	716 – 771	716 – 771
Week 112 ¹	785	>771	>771
4-week after EOT ²	785 ¹ or Last Dose Date + 28 ³	>771 ¹ or 2-12 weeks (14-84 days) after Date of Last Dose ³	>771 ¹ or 2-12 weeks (14-84 days) of Date of Last Dose ³

¹ For patients who completed the planned randomized treatment period.

² Efficacy endpoints only.

³ For patients who discontinued the randomized treatment early.

eGFR = estimated glomerular filtration rate; EOT = End of Treatment; N/A = not applicable.

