standing for 1 minute, and 1 time after the patient has been standing for 3 minutes. Weight, heart rate, temperature, and respiration rate will also be recorded. For patients <18 years of age, height will be measured every 6 months until the patient turns 18.

- ^d Except for Week 114 (see footnote e), Includes clinical chemistry (sodium, potassium, chloride, bicarbonate, total protein, albumin, calcium, phosphate, glucose, cystatin, uric acid, BUN, creatinine [including calculation of eGFR], bilirubin [total, direct, and indirect], ALT, AST, ALP, gamma glutamyl transferase, creatine kinase, and amylase); lipid panel (total cholesterol, LDL [direct], HDL [direct], and triglycerides [direct]); hematology (red blood cells, hemoglobin, hematocrit, MCV, MCH, MCHC, platelets, WBC and WBC differential [neutrophils, eosinophils, basophils, lymphocytes, and monocytes, % and absolute]). All chemistry, hematology, and lipid analytes are shown in [Section 15.2.4](#).
- ^e Includes only serum creatinine and serum potassium.
- ^f NT-proBNP in patients ≥ 18 years of age only.
- ^g Urine total protein, creatinine, and microalbumin. The patient will collect the first morning void within 5 days prior to the visit and bring the sample to the site visit.
- ^h Patients ≥ 18 years of age will complete the KDQOL instrument, and patients <18 years of age will complete the PedsQL QoL questionnaire. All patients will also complete the EQ-5D. If the questionnaires were NOT completed at Week 112 (ie, Visit 17), the patient should not complete them for the rest of the open-label extension.
- ⁱ Urine pregnancy tests will be dispensed to WOCBP to conduct pregnancy testing at home between study visits. Site will provide the patient enough tests to conduct pregnancy testing once per month until the next scheduled study visit and will contact these patients monthly to confirm that the pregnancy test has been performed and the results are negative. A positive urine pregnancy test will be confirmed by a serum test. At every visit and monthly, sites will verify that WOCBP are continuing to use highly reliable contraception methods.

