8. EFFICACY

8.1. General Considerations

All efficacy analyses will be based on the FAS or IAS, as described below. The primary, surrogate, and secondary endpoint analyses will also be performed on the PP Analysis Set as supportive analyses. All primary efficacy analyses based on laboratory data will use central lab data only. All efficacy analyses specified below refer to the double-blind period only.

UP/C will be determined using first morning void urine samples and will be calculated as the geometric mean of 3 first morning void urine samples collected within 5 days prior to the visit. If one of the samples is missing, the average of the other 2 samples will be used. As UP/C is a highly right-skewed variable, analyses will be performed on log-transformed data. For ease of interpretation, results will be presented in the original units.

The eGFR for each baseline and post-baseline visit will be determined using the CKD-EPI (Levey 2009) formula for patients ≥ 16 years of age at the time of screening and the Modified Schwartz formula for patients < 16 years of age at the time of screening (Schwartz 2009a; Schwartz 2009b).

For the purposes of efficacy analyses, an assessment is considered “on treatment” if it occurs after the first dose of study medication and no more than 3 days after the date of last dose of randomized treatment.

For all least-squares (LS) means that include strata coefficients, the observed strata proportions will be used instead of assuming equal sizes of strata.

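### For treatment completers, the Week 112 window in SAP Table 2 is not tied to the last randomised dose, so an on-drug or too-early eGFR can be analysed as the post-cessation value

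*SAP*

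**What the plan says.** SAP 6.5.4, Table 2, gives Week 112 a target of Day 785 and a window of every day after Day 771, with no upper limit. A footnote limits the row: "For patients who completed the planned randomized treatment period". When several values fall in a window, unscheduled ones included, "the value closest to the target day for that visit will be selected for analysis". On ties: "If more than 1 assessment is equidistant to the target day, then the latest value will be selected".

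Drug status is addressed once: "For efficacy analysis visits on or prior to Week 108, only assessments while the patient is on randomized treatment should be included". Week 112 has no matching off-treatment condition. Patients who stop early are treated differently. Their 4-week-after-EOT value is targeted at last dose + 28 days, in a window of "2-12 weeks (14-84 days) after Date of Last Dose". For completers, that same row repeats Day 785 and >771.

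The selected value is the dependent variable in the analyses of covariance in SAP 8.7.2 (absolute change) and 8.7.3 (percent change). Both restrict patients to those who completed the 108 weeks of treatment. Neither restricts assessments by time since last dose. Under SAP 8.4, absolute change is the last step of the US hierarchy, and percent change is one of three Holm-tested secondary endpoints elsewhere.

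On scope, Table 2 is introduced with "The following visit windows for the double-blind period are defined for endpoints based on laboratory results", and open-label windows are left to a separate SAP. SAP 8.1 adds "All efficacy analyses specified below refer to the double-blind period only". Protocol 6.2.2 places every Week 112 evaluation before the first open-label dose.

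**The concern.** The endpoint is named for a time relative to stopping randomised drug, but its window is fixed in days since the first dose. The two agree only if treatment stops close to schedule and no other eGFR lies nearer Day 785. When either condition fails, the stated rule can select a value taken on randomised drug, or well short of four weeks after it. The patient stays in the analysis with that value labelled Week 112.

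At stake is an endpoint inside the multiplicity procedure in both regions. If on-drug and off-drug eGFR differ by different amounts in the two arms, misassigned values shift the treatment contrast.

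**Working it through.** **Inputs.** Target days, windows and selection rules are from SAP Table 2 and 6.5.4. Visit windows are from Protocol Table 1: Week 108 ±7 days, and Week 112 −7 to +14 days. The definition of on treatment, up to 3 days after the last dose, is from SAP 8.1. The repeat central-laboratory eGFR before Week 112 is allowed by Protocol 7.2.2, criterion 4.

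**1. Reproduce Table 2.** Target day = 7 × week + 1, so Week 108 is Day 757 and Week 112 is Day 785. The cut is the midpoint: (757 + 785)/2 = 771. The same rule reproduces the table's other eGFR cuts from Day 22 onward.

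**2. Delayed Week 108 visit.** Let the Week 108 visit and last dose both fall on Day D > 771, with Week 112 on Day D + 28. The distances from target are |D − 785| and |D + 28 − 785| = D − 757.
- For D ≤ 785, the on-drug value is nearer when 785 − D < D − 757, that is, when D > 771. This always holds here.
- For D > 785, D − 785 < D − 757 always.

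So the on-drug value is selected every time. For D = 775 the distances are 10 days (Day 775) and 18 days (Day 803). If the gap is 21 days, selection of the on-drug value starts at D = 775.

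**3. How late that is.** The Week 108 window is Days 750-764. The first affected day, 772, is 772 − 757 = 15 days after target and 772 − 764 = 8 days outside the window. A Week 108 visit inside its window cannot enter Week 112.

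**4. A case inside the protocol windows.** Take Week 108 and last dose on Day 764, a repeat eGFR on Day 774, and Week 112 on Day 799 (785 + 14). The repeat is |774 − 785| = 11 days from target and the true visit is |799 − 785| = 14, so the repeat is selected. It was taken 774 − 764 = 10 days after the last dose; the true visit was 35 days after.

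**5. Sensitivity analysis.** SAP 8.7.2 and 8.7.3 check robustness with the 4-week-after-EOT visit. For completers that row uses the same target and the same >771 window, so steps 2 and 4 give the same selections.

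**6. Size.** Shift in the contrast ≈ share misassigned × between-arm difference in the on-drug versus off-drug shift. Neither factor is in the documents. The assumed ranges are 2-10% and 1-5 mL/min/1.73 m².
- Low: 0.02 × 1 = 0.02 mL/min/1.73 m².
- Middle: 0.05 × 3 = 0.15 mL/min/1.73 m².
- High: 0.10 × 5 = 0.5 mL/min/1.73 m².

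As a rough yardstick, the projected total-slope difference in SAP 4.3.1.2 is 2.1 per year, or about 2.1 × 2 = 4.2 mL/min/1.73 m² over two years. The middle case is 0.15/4.2, under 4% of that.

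**The case against.** A reader might infer that open-label sparsentan values can also enter. Week 114 collects creatinine (Protocol Table 6: "Includes only serum creatinine and serum potassium"). With Week 112 on Day 778 and Week 114 on Day 792, both are 7 days from target and the tie rule takes the later. The documents do not support that reading. Table 2 is stated to cover the double-blind period, SAP 8.1 limits efficacy analyses to that period, and the protocol completes Week 112 before open-label dosing. What remains is that these sentences are not written as a date cut in the window. The SAP does write one elsewhere, in 6.4.2 for the open-label baseline and in 10.1.3 for on-treatment adverse events.

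A second tempting inference is that on-drug values simply restore the acute drug effect that the endpoint was designed to remove. No passage states that purpose. Protocol 6.2.1 also has standard care, including RAAS inhibitors unless contraindicated, resumed at Week 108. Week 112 is therefore generally measured on replacement therapy, and only a net difference between arms matters.

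The best defence of the plan is rarity and intent. Step 2 needs a Week 108 visit well outside its window. The endpoint's name makes the intent plain, and the Per Protocol repeat may remove some cases, since SAP 7.3 lists extensive visit-window violations among possible major deviations. The rarity argument stands and lowers the importance. It does not cure the rule: the Full Analysis Set keeps these patients, and the case in step 4 involves no window violation.

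**Conclusion.** The concern holds as a minor point. For completers, Table 2 as written can assign to Week 112 an eGFR taken on randomised drug, or about 10 days after it. In the four-week delayed-visit case it does so every time. This assumes that dosing continued to the delayed visit and that both values are available.

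The effect is probably small. Few patients are likely to meet either condition, and the 0.02-0.5 mL/min/1.73 m² range rests wholly on assumed shares and shifts. The documents do not establish its direction. The primary slope analyses do not use Week 112. The endpoint is secondary in both regions, and the documents do not call it key.

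**What to change.** In SAP Table 2, for both the Week 112 row and the completer part of the 4-week-after-EOT row, select the value nearest last randomised dose + 28 days. Require it to lie 14-84 days after that dose and on or before the first open-label dose (pre-dose). This is the rule already used for early stoppers plus one date cut.

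Checked against the cases above:
- With last dose on Day 772, 775, 785 or 790 and a visit 28 days later, the off-drug value is selected each time.
- With last dose on Day 757, Week 112 on Day 778, 780 or 785, and Week 114 two weeks after that, the pre-open-label value is selected each time.
- In the Day 764/774/799 case, the repeat is excluded (10 days is less than 14) and Day 799 is used (35 days).

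The cost is an edit to two table rows and a footnote, with no change to visits or procedures. The downside is that a few completers with no qualifying value would drop out of this analysis.

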6.1.3. Open-Label Endpoints

Endpoints for the open-label extension include, but are not necessarily limited to:

- The absolute and percent change from Week 112 in eGFR at each visit
- The percent change from Week 112 in UP/C at each visit
- Changes from Week 112 in QoL at each visit
- Changes from Week 112 in body weight, vital signs, physical examinations, peripheral edema, and clinical laboratory parameters

- Changes from Week 112 in lipid profile (total cholesterol and triglycerides, LDL-C, and HDL-C)
- The incidence of TEAEs during the open-label extension

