^f Following the 108-week blinded treatment period, treatment with study medication will be discontinued and patients may be evaluated for eligibility in the open-label extension. At this time, the Investigator should resume standard-of-care treatment, including treatment with RAAS inhibitors provided there are no contraindications for their use. If the patient was treated with irbesartan at study entry, an alternative ARB at an equivalent dose is required from Week 108 to Week 112. The Investigator may make additional adjustments in antihypertensive medications as necessary to adequately control the patient's blood pressure.

Table 1: Study 021FSGS16010 Double-Blind Study Visits

	Visit 1 ^a	Visit 2 (± 3 days)		Visit 3 ^d	Visit 4 (± 3 days)	Visit 5 (± 3 days)	Visit 6 (± 7 days)	Visit 7 (± 7 days)	Visit 8 (± 7 days)
Visit:	Screening All Patients	Washout Patients ^b		Blinded Treatment					
Week :	W -6	W - 2 ^b	W-1 ^c	Day 1 (Randomization)	W2	W4	W6	W8	W12
	Visit 9 (± 7 days)	Visit 10 (± 7 days)	Visit 11 (± 7 days)	Visit 12 (±7 days)	Visit 13 (±7 days)	Visit 14 (±7 days)	Visit 15 (±7 days)	Visit 16^e (±7 days)	Visit 17 (-7 to +14 days)
Visit:	Blinded Treatment								End of Double-Blind Period Visit
Week :	W24	W36	W48	W60	W72	W84	W96	W108	W112

^a The screening period for all patients is 6 weeks (42 days) prior to Day 1. Under extenuating circumstances, the screening period may be extended by a maximum of 2 weeks.

^b Patients taking RAAS inhibitors at screening (Visit 1) will complete a 2-week (14-day) washout from these medications prior to Day 1 (Randomization). The washout should begin no later than 4 weeks (28 days) after Visit 1.

^c Patients undergoing washout will return to the clinic for a follow-up visit to assess safety and blood pressure control approximately 1 week after the start of the washout period.

^d The Day 1 (Randomization) Visit will occur no later than 6 weeks (42 days) after Visit 1 (8 weeks if the screening period was extended). All eligible patients will be randomized via interactive web response system (IWRS) and the first dose will be administered in the clinic.

^e Visit 16 is the End of Treatment visit.

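### SAP 6.5.4 requires every urinalysis replicate to be on study medication, with no Week 108 limit, which empties the Week 112 and post-treatment UP/C windows that its own Table 2 defines

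*SAP*

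**What the plan says.** SAP 6.5.4 (Visit Windows) contains two on-treatment rules in successive paragraphs.

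- The general rule has a limit: "For efficacy analysis visits on or prior to Week 108, only assessments while the patient is on randomized treatment should be included".
- The replicate rule covers urinalysis endpoints formed as a geometric mean of several samples. It says the replicates must map to one analysis visit, and that they "should be within 5 days of each other, and should all have been collected while the subject was on study medication". No visit limit is attached.
- The only exception follows at once: "For the derivation of baseline, all replicates must have been collected on or prior to the date of reference dose".

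SAP 8.1 counts an efficacy assessment as on treatment if it is "no more than 3 days after the date of last dose of randomized treatment".

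Table 2, also in SAP 6.5.4, gives quantitative urinalysis a Week 112 window (after Day 771, for patients who completed randomized treatment). It also gives a 4-week after EOT window, which for early discontinuers is "2-12 weeks (14-84 days) of Date of Last Dose". A footnote reserves the latter for efficacy endpoints.

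In the protocol, Table 5 schedules three first-morning voids at Week 112, which Section 6.2.1 makes the last visit of the double-blind period. UP/C percent change by visit is an exploratory endpoint (Protocol 6.1.1.3, SAP 3.2.3), and Protocol 12.7.3 applies the log UP/C model to every post-baseline double-blind visit.

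**The concern.** The Week 112 and post-EOT windows exist to hold values taken after randomized treatment has stopped. A rule that admits only samples taken on study medication cannot fill them. A programmer who follows the sentence leaves both urinalysis windows empty; one who follows the table breaks the sentence. The SAP does not say which takes precedence.

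At stake are the derived Week 112 and post-EOT values of UP/C and of any other urinalysis parameter averaged over replicates. Dropping them would also depart from Protocol 12.7.3 without saying so: SAP 5.4 lists a single departure from the protocol, and it concerns the interim analysis population.

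**Working it through.** There is no sample-size, power or alpha figure to reproduce. The check is study-day arithmetic.

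**Inputs**

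| Item | Value | Source |
|---|---|---|
| Week 108 target day and visit window | Day 757, ±7 days | SAP Table 2; Protocol Table 1 |
| Week 112 target day and visit window | Day 785, −7 to +14 days | SAP Table 2; Protocol Table 1 |
| Sample timing | three mornings within the 5 days before the visit | Protocol Table 5, footnote e |
| On-treatment limit | last dose + 3 days | SAP 8.1 |
| Week 112 urinalysis window | after Day 771 | SAP Table 2 |
| 4-week after EOT window, early discontinuers | 14 to 84 days after last dose | SAP Table 2 |

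Assumption: the last dose is taken on the day of the Week 108 visit, within its window.

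**Week 112**

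1. Last dose: 757 − 7 = Day 750 to 757 + 7 = Day 764.
2. Latest on-treatment day: 764 + 3 = Day 767.
3. Visit: 785 − 7 = Day 778 to 785 + 14 = Day 799.
4. Samples: 778 − 5 = Day 773 to Day 799.
5. Smallest gap between a sample and the end of on-treatment status: 773 − 767 = 6 days.
6. All combinations: 15 last-dose days × 22 visit days × 6 sample days = 1,980. None meets the clause.
7. For the earliest day in the window, Day 772, to count as on treatment, the last dose would have to be on Day 772 − 3 = Day 769 or later. That is outside the Week 108 visit window.

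The 3-day rule is not essential to this. Protocol 8.3.1 describes the 4 weeks before the open-label extension as free of study medication.

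**4 weeks after EOT, early discontinuers**

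The window has 84 − 14 + 1 = 71 days. The earliest is 14 days after last dose, against a limit of 3, so 0 of 71 qualify. For treatment completers this window is the Week 112 window, with the result above.

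**Other rules that might rescue the values**

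The single-sample provision in SAP 6.5.4 applies when only one sample is available within 5 days. It does not cover samples excluded because of treatment status.

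**Open-label baseline**

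The on-medication clause cannot govern baseline. If it did, no double-blind baseline UP/C could be formed, since those samples precede the first dose. The baseline sentence must therefore replace it. With the first open-label dose at the Week 112 visit, all 22 × 6 = 132 visit and sample-day combinations fall on or before that dose and qualify.

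**After the fix**

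With the clause limited to visits through Week 108, all in-schedule Week 112 samples (Days 773 to 799) and all 71 post-EOT days become eligible. The open-label baseline does not change.

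**The case against.** The best defence is that the intent can be recovered. The preceding paragraph carries the Week 108 limit, and Table 2 would be pointless for urinalysis after Week 108 unless the replicate sentence carried it too. That is probably what was meant. It is still an inference against the words, and the sentence gives an empty result when followed.

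A second defence is that little depends on these values. The partial-remission endpoint is modelled through Week 60 at the interim and Week 108 at the final analysis (SAP 8.6.1). The Week 112 secondary endpoints are eGFR, which is not a replicate mean, and SAP 8.7.2 and 8.7.3 use the post-EOT visit for eGFR only. This stands and limits the point. It is less clear that the by-visit UP/C model stops at Week 108. SAP 8.8.2.2 leads back through 8.8.1.4 to 8.7.1, which runs from Week 2 to Week 108. But 8.8.1.3 also calls its model analogous to 8.7.1 and runs it to Week 112, so that label does not fix the visit range.

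Three stronger readings are tempting, and the documents do not support them.

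- **The open-label UP/C baseline falls back to Week 108.** A reader might infer this from SAP 6.4.2, which takes the "last non-missing assessment prior to and including the first administration of sparsentan", if Week 112 were missing. It is not missing for that purpose, because the baseline sentence admits the Week 112 samples. Protocol 6.2.2 names Week 112 as the open-label baseline, and the endpoint is "The percent change from Week 112 in UP/C at each visit". SAP 5.3 also defers the final open-label analysis to a separate plan.
- **Three samples from each of about 300 patients are lost.** The Week 112 analysis visit covers treatment completers only. The samples are still collected and individual data still listed (SAP 6.1); only the derived mean is affected.
- **The trial loses its test of whether the antiproteinuric effect reverses.** Neither document gives Week 112 UP/C that role. Standard care, including RAAS inhibitors where not contraindicated, resumes at Week 108 (Protocol 6.2.1), so Week 112 is off randomized drug but not untreated.

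**Conclusion.** The contradiction is real and its reach is small. Taken literally, SAP 6.5.4 excludes every in-schedule Week 112 and 4-week post-EOT value of UP/C and of other replicate-derived urinalysis parameters: 0 of 1,980 day combinations and 0 of 71 days qualify. Table 2 and the protocol's by-visit UP/C analysis both call for values there.

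The consequence is confined to exploratory or descriptive urinalysis after Week 108. No primary, surrogate or formal secondary result changes, and the open-label baseline is unaffected. The documents give no basis for attaching an effect size.

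The Week 112 result assumes that last dose, visit and samples fall within the scheduled windows; a last dose on Day 769 or later could produce an exception. The open-label conclusion assumes that the reference dose, which SAP 6.5.4 does not define, means the first open-label dose when the open-label baseline is derived.

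**What to change.** Make two edits to SAP 6.5.4.

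1. Limit the on-medication condition for replicates to analysis visits on or before Week 108, matching the general filter. State that Week 112 and 4-week after EOT replicates are taken in their Table 2 windows and before any open-label dose. The second part is useful because the window after Day 771 has no stated upper end.
2. Define the reference dose as the first double-blind dose or the first open-label dose, according to which baseline is being derived.

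SAP 6.4.2 needs no change; its last-non-missing rule already works. The cost is one clause and one definition, with no new data, visits or analyses. If the datasets are already built, the study report should state which reading was programmed.
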